4.4.2 Data Collection and Follow-up for Withdrawn Subjects

Even though subjects may be prematurely withdrawn from the study, it is imperative to collect infection data (microbiology swabs) or symptomatic data. Such data is important to the integrity of the final study analysis since early withdrawal could be related to the tolerability profile or the ineffectiveness of the therapy. If a subject withdraws consent to participate in the study, attempts should be made to obtain permission to follow up with the subject's CRS for the duration of the 12-week follow-up period. Subjects with incomplete/missing data will not be included in the analysis.

5 Study Drug

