4.4 Early Withdrawal of Subjects

4.4.1 When and How to Withdraw Subjects

Subject may be withdrawn from the study prior to the expected completion of the protocol if the subject fails to adhere to protocol requirements, subject withdraws consent, or symptoms of acute rhinosinusitis exacerbation persist. Subjects will return to routine clinical care at that point.

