6.5 Statistical Methods

Data will be analyzed after 100 subjects have completed the study. Descriptive demographic data will be compiled including mean and median age, adjuvant therapy use, use of oral antibiotics, and microbiome profile. Longitudinal linear mixed effects modeling will be used to examine the relationship between all outcome measures and treatment assignment, assuming that the distribution of the outcome measures follow a unimodal symmetric distribution and satisfies the assumptions for mixed effects modeling. Mixed effects modeling takes advantage of all available data (up to the point of loss to follow-up or withdrawal) and also can address missing data. As long as the level of missingness is not excessive and patterns of missingness are not detected, mixed effects modeling can use all available data.²¹⁻²⁴ For all analyses, alpha will be set to 0.05 (two-sided).

The Epidemiology Department may be consulted at the completion of the study to assist with data analysis. Only de-identified data will be provided. No PHI will be shared.

CONFIDENTIAL

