6.6 Subject Population(s) for Analysis

All-randomized population: Any subject randomized into the study, regardless of whether they received study drug, will be analyzed.

7 Safety and Adverse Events

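### Section 4.4.2 drops subjects with incomplete data, against the all-randomized, all-available-data analysis in 6.5 and 6.6, and so can remove treatment failures

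*Combined protocol and SAP*

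**What the plan says.** Three sections define who is analysed.

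- **4.4.2**, on follow-up of withdrawn subjects: "Subjects with incomplete/missing data will not be included in the analysis".
- **6.6**, on the analysis population: "Any subject randomized into the study, regardless of whether they received study drug, will be analyzed".
- **6.5**, on methods: "Mixed effects modeling takes advantage of all available data (up to the point of loss to follow-up or withdrawal". Reliance on all available data is conditional: "As long as the level of missingness is not excessive and patterns of missingness are not detected". No alternative is given if the condition fails.

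Section 4.4.1 sets out when a subject leaves: "Subject may be withdrawn from the study prior to the expected completion of the protocol", on grounds that include "subject withdraws consent, or symptoms of acute rhinosinusitis exacerbation persist". It adds: "Subjects will return to routine clinical care at that point". Section 4.4.2 also explains why data on these subjects are needed: "early withdrawal could be related to the tolerability profile or the ineffectiveness of the therapy". Sections 2.1 and 3.2 place the need for antibiotics among the primary outcomes, beside SNOT-22, endoscopy and culture.

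**The concern.** A subject with baseline and week-4 data but no week-12 visit is excluded by 4.4.2 and included by 6.5 and 6.6. The exclusion is not confined to a secondary analysis, and the text does not say whether it works per subject or per outcome. Section 4.4.2 also undercuts itself: it asks for data because withdrawal may signal failure, then discards the subject if the record stays incomplete.

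The rule selects subjects on an event after randomization that can depend on both treatment and outcome, so the comparison no longer rests on randomization. All four primary outcomes are exposed, rescue antibiotics most directly. Under 7.4 the lead investigator receives the full allocation log when the study is ready for analysis, so an unresolved conflict could be settled with the arms known.

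**Working it through.** **The plan's own figure.** Section 6.4 gives SD 20, a 95% CI half-width of 10 and 32 per group. For a difference of two means, n = 2 × (1.96 × 20 / 10)² = 30.7, so 31 per group. With the t quantile on 2n − 2 degrees of freedom the smallest n is 32 (half-width 9.99). The figure reproduces and is not in dispute. The surplus up to 100 protects precision only; it does not remove selection bias.

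The documents give no withdrawal or rescue rates. All rates and correlations below are assumptions, used to illustrate and not to bound.

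**Illustration 1: rescue antibiotics.** If the true failure rate is p and a fraction f of failures is dropped, the observed rate is p(1 − f) / (1 − pf). Take p = 20% on quinine and 40% on placebo.

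| f | Quinine | Placebo | Difference (points) | Subjects lost (quinine / placebo) |
|---|---|---|---|---|
| 0 | 20.0% | 40.0% | 20.0 | 0% / 0% |
| 0.25 | 0.15/0.95 = 15.8% | 0.30/0.90 = 33.3% | 17.5 | 5% / 10% |
| 0.50 | 0.10/0.90 = 11.1% | 0.20/0.80 = 25.0% | 13.9 | 10% / 20% |
| 1 | 0% | 0% | 0 | 20% / 40% |

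**Illustration 2: SNOT-22, no drug effect.** Scores have SD 20 (6.4). The worst 20% on quinine and the worst 10% on placebo at week 4 miss week 12. After the worst fraction q is removed, the mean shifts by −20 × φ(z) / (1 − q), with z the 1 − q normal quantile.

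- q = 0.20: −20 × 0.2800 / 0.80 = −7.00
- q = 0.10: −20 × 0.1755 / 0.90 = −3.90
- False week-4 difference, quinine minus placebo: −7.00 − (−3.90) = −3.10. It becomes +3.10 if the loss rates swap, and 0 if they are equal.
- With between-visit correlation 0.5, baseline and week 12 each shift by 0.5 × (−3.10) = −1.55. As change from baseline the bias is −3.10 − (−1.55) = −1.55 at week 4 and 0 at week 12.
- With correlation 0.3 or 0.7, the week-12 score difference is −0.93 or −2.17.

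**Same data under the two rules.** Simulation with 400,000 per arm, three visits and correlation 0.5:

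| Rule | Week 4 | Week 12 |
|---|---|---|
| Complete records only (4.4.2) | −3.05 | −1.52 |
| All available data, maximum likelihood (6.5) | 0.08 | 0.02 |

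A random-intercept mixed model with 4,000 per arm agrees: −0.15 (SE 0.45) and 0.13 (SE 0.48) with all data; −2.88 and −1.25 (SE 0.45 each) with complete records only.

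**Where 6.5 also fails.** If the same subjects miss week 4 as well as week 12, loss depends on scores never recorded. All-available-data likelihood is then biased by roughly −2.6 at week 4 and −0.9 at week 12, against −3.1 and −1.5 for complete records.

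**The case against.** The conflict in wording is not disputed. The case against its weight has five parts.

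- **Scale.** Section 3.2 names change in SNOT-22. On that scale illustration 2 gives −1.5 and 0, well inside the 95% half-width of 1.96 × 20 × √(2/50) = 7.8 (8.3 at 45 per arm). This is fair on size. A wide interval does not make a biased estimate acceptable, however, and illustration 1 does not depend on that scale.
- **Mechanism.** Double the loss on quinine with no drug effect has no documented cause, and 5.1 matches the placebo for bitterness. This works against taste-driven differential loss. If quinine works, failure rates differ and illustration 1 applies.
- **How often the rule bites.** Withdrawal is permissive and antibiotics can be started without it (5.6). SNOT-22, endoscopy and culture are listed as clinical care (section 6), so many records may be completed. Conversely, 3.1 ties traditional swabs to visible pus, so a literal per-subject reading could also drop subjects who cleared. Both points stand. The second is a further reason for not leaving the rule as written.
- **Precedence.** Sections 6.5 and 6.6 are the natural home of the analysis rule. Placement suggests that they were meant to govern, but no text says so.
- **The remedy is partial.** Deleting the sentence removes little bias when both later visits are missing. This is correct, and it is why a sensitivity analysis for informative withdrawal is needed as well.

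**Conclusion.** The concern holds and must be fixed. The contradiction is in the current text and is certain. It leaves the analysis set undetermined for every primary comparison, and one of the two readings selects on a possible consequence of treatment.

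The size and direction of any bias are not known. On the assumed rates, a true 20-point rescue difference falls to 17.5 or 13.9 when a quarter or half of failures are dropped. A null SNOT-22 effect can appear as about −3.1 at week 4 on the score scale, or −1.5 as change from baseline, with the sign set by which arm loses more. The advantage of the 6.5 model over complete records holds only when missingness depends on recorded scores.

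**What to change.** Required:

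1. Delete the last sentence of 4.4.2.
2. State in 4.4.2, 6.5 and 6.6 alike that the primary analysis includes all randomized subjects by assigned arm, with the mixed model using every available visit. The first 10 subjects, who under 4.3 are not randomized, fall outside that set.
3. Count rescue antibiotics recorded for withdrawn subjects, within the permissions in 4.4.2 and 8.1.
4. Keep a completers-only analysis, labelled as a sensitivity analysis.
5. Add one sensitivity analysis for informative withdrawal, for example counting withdrawal for persistent symptoms as need for rescue. Section 6.5 has no fallback if patterns of missingness are found.

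Whether symptom data collected after withdrawal enter the primary model is an estimand choice, to be stated before unblinding. The clinical withdrawal rule is not judged here.

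Cost: one sentence deleted, wording aligned in three sections, and two labelled sensitivity analyses. No added patients, visits or procedures; 32 per group and the total of 100 are unchanged.

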5.1 Description

IDS will compound 0.9% buffered sterile NaCl for irrigation with USP grade quinine to a 1mg/ml concentration. For the placebo arm, IDS will compound 0.9% sterile NaCl for irrigation with sucrose octaacetate (0.5mg/ml) to achieve the same degree of bitter taste as 1mg/ml concentration of quinine¹⁹.

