1.4 Clinical Data to Date

In a 2001 study by Desrosiers et al¹⁶, topical tobramycin was being evaluated for efficacy in medically recalcitrant bacterial sinusitis. In order to blind the control group, quinine was added to saline to mimic the bitter taste of tobramycin. Patients were treated with nasal solutions three times per day for 4 weeks. Interestingly, both treatment arms demonstrated clinical improvement, with the saline+quinine arm demonstrating comparable if not better efficacy to topical tobramycin with no adverse events reported in the study. These findings were surprising and “unexplained” to the authors at the time. We now believe that the quinine in their “control” group stimulated airway bitter taste receptors to stimulate sinonasal nitric oxide production to eradicate the infection. We should also mention that tobramycin does not stimulate NO production in primary human sinonasal epithelial cells.

Additionally, safety of quinine administration is further supported by a prior 1993 study that utilized quinine to determine compliance with nebulized tobramycin in the management of CF pseudomonas¹⁷. In this study the pharmacokinetics of inhaled tobramycin was evaluated. To assess compliance with the protocol both the tobramycin and placebo arms were spiked with quinine (1mg/ml) and urine quinine concentrations were checked. No adverse events were reported for the use of quinine in the airway.

Thus, we propose to repeat the Desrosiers study, but to instead evaluate quinine as a therapeutic agent, not a placebo, and directly compare quinine to saline (spiked with Sucrose Octaacetate). Truth be told, we stumbled onto the biologic effect of quinine in the search for a bitter compound to use in a randomized trial with another bitter compound. Surprisingly, quinine stimulated a more robust NO response than our original compound of interest (phenylthiocarbamide). Subsequently, we discovered the 2001 Desrosiers study that further supported the concept of quinine as a topical therapy for bacterial sinusitis.

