3.2 Primary Study Endpoints

- Efficacy of quinine and saline irrigations compared to saline irrigations alone.
- Changes in quality of life (SNOT-22 questionnaire) (both composite and subscale scores)
- Nasal endoscopy (Lund-Kennedy Score)
- Alterations in microbiology recovered (as determined by sinus microbiology culture)
- Whether or not conventional antibiotics were needed to treat the infection during or following the irrigation trial (as prescribed as part of routine care)

CONFIDENTIAL

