4.3 Subject Recruitment and Screening

All study personnel will be appropriately trained and certified according to their role in the study and duties, including HIPAA and CITI training.

Subjects will be identified and approached as they present to clinic for their routine treatment for chronic rhinosinusitis. Subjects will be brought into a private clinical examination room where a clinical research nurse will explain the protocol in detail. Subjects will have the time to ask and have questions answered about the research prior to signing the consent form.

Patients interested in enrolling in the study will be instructed on how to administer the solutions using a 3cc syringe with an atomizer and have the opportunity to trial this technique with isotonic buffered saline under direct supervision of the treating physician or research coordinator. Patients who feel that they can adequately self-administer the solution will be asked to participate in the study.

Subjects who withdraw or are otherwise not interested in the protocol will have access to the ENT clinic for their regular care. They will be reminded that their care (and if applicable, employment, or student status at Penn) will in no way be affected by their decision to participate in the protocol or not.

As per FDA recommendation, the first 10 patients enrolled into the study will be placed into the treatment arm, and will not be randomized. The purpose of this is to make sure that the treatment is efficacious enough to rationalize going forward with the trial. This will not affect the ICF, as the patient will not be aware of this forced assignment into the treatment arm (i.e. they will still be blinded to their assignment).

CONFIDENTIAL

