5.7 Packaging

1 mg/ml concentration of quinine in saline solution will be given to participants to instill in each nostril. Product will be packaged in 90mL amber glass boston rounds, which have been autoclaved prior to use. A pharmaceutical press-in bottle adapter will be inserted into the neck and a child-resistant cap tightly placed onto the bottle. Doses will be administered by use of an LMA® MAD NASAL™ Intranasal Mucosal Atomization Device with 3mL syringe and vial adapter (Teleflex Medical, Research Triangle Park NC; item # MAD140OS), which is patient-specific. Participants will do this twice per day for 4 weeks. Subjects will clean the mucosal atomization device after each use with an alcohol swab.

Blinding of Study Drug

The placebo arm will be spiked with Sucrose Octaacetate which has a bitter taste, but does not stimulate sinonasal NO production.

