6.1 Visit 1 (week 0)

Patients who consent to participate will be randomized to a treatment arm of quinine and saline (1mg/ml) or sucrose octaacetate (0.5mg/ml) in saline as dispensed by IDS. The study nurse coordinator will instruct the patient on how to administer the solution.

Following the routine endoscopically guided sinus culture swab, an additional research microbiome swab will be obtained. Patients will be asked to complete a routine Sinonasal Outcomes Test (SNOT-22) questionnaire as well as undergo a Sniffin' Stick Test as part of the research. Additionally, as part of their initial clinical assessment, a nasal endoscopy will be performed and recorded. This will later be scored by a blinded clinical investigator. If a CT scan of the sinuses is clinically indicated, then one will be performed. Additionally, a taste test to determine bitter taste sensitivity will be administered. This taste test is comprised of non-toxic solutions which are not swallowed by the patient.

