6.4 Sample Size Determination

There is no prior data to base a power calculation on. This trial will utilize a total of 100 patients to help guide future studies with appropriate power. In order to determine this sample size, we utilized a calculation that would ensure us that our confidence interval has a specified width. A previous study sampled over 300 CRS patients and found pre- and post-surgical SNOT-22 scores to have a standard deviation of about 20²¹. Based on this prior work, we estimate the required sample size to detect an effect with a precision of 10 (half the width of the desired 95% CI) to be 32 patients in each group. We will therefore recruit a total of n=100 patients in order to provide a margin for error, early withdrawal, or non-compliance.

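### Section 5.1 describes the quinine vehicle as buffered saline and the placebo vehicle only as saline; the two sentences need reconciling so that the arms are stated to differ in the bitter agent alone

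*Combined protocol and SAP*

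**What the plan says.** Section 5.1 (Description) specifies the two products in consecutive sentences. For the active arm: "IDS will compound 0.9% buffered sterile NaCl for irrigation with USP grade quinine to a 1mg/ml concentration". For the control arm: "For the placebo arm, IDS will compound 0.9% sterile NaCl for irrigation with sucrose octaacetate (0.5mg/ml", a strength chosen to match the bitterness of the quinine solution. Both are 0.9% and sterile. Only the quinine vehicle is called buffered.

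Elsewhere the carrier is simply saline. Section 1.4 says the trial will "directly compare quinine to saline (spiked with Sucrose Octaacetate" (the quote stops just before the closing bracket). Section 3.2 gives the efficacy contrast as "Efficacy of quinine and saline irrigations compared to saline irrigations alone". Section 6.1 has patients "randomized to a treatment arm of quinine and saline (1mg/ml) or sucrose octaacetate (0.5mg/ml) in saline as dispensed by IDS". Sections 5.2 and 5.7 and the procedures table in Section 6 also mention saline without qualification.

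Buffered saline appears in one other place, Section 4.3, where interested patients "have the opportunity to trial this technique with isotonic buffered saline under direct supervision". That is technique practice before enrolment, not a trial product.

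The blinding paragraph under Section 5.7 says: "The placebo arm will be spiked with Sucrose Octaacetate which has a bitter taste, but does not stimulate sinonasal NO production". It deals with the additive and is silent on the vehicle.

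**The concern.** The aim in Sections 1.4 and 3.2 is to learn what quinine adds to saline. That requires the saline to be the same in both arms, apart from the sucrose octaacetate that is deliberately added to the placebo for taste. Section 5.1, read literally, gives the pharmacy two vehicles.

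If the products were made that way, the difference between arms in SNOT-22, endoscopy score, culture or need for antibiotics would be the effect of quinine plus whatever buffering does. Those are the primary endpoints of Section 3.2. A difference built into the products is not a chance imbalance, so randomization cannot be expected to even it out.

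**Working it through.** **Vehicle wording, section by section**

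| Section | Quinine arm | Placebo arm |
|---|---|---|
| 5.1 Description | 0.9%, sterile, buffered | 0.9%, sterile; buffering not mentioned |
| 6.1 Visit 1 | saline | saline |
| 3.2 Primary Study Endpoints | saline | saline |
| 1.4 Clinical Data to Date | vehicle not named | saline |
| 5.7, blinding paragraph | not mentioned | additive only |

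Only Section 5.1 is specific enough to compound from. The unqualified references elsewhere fit a common vehicle, but they fit two different salines as well, so they do not settle the question.

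**Other qualifiers in the same two sentences**

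Section 5.1 gives a USP grade for quinine and none for sucrose octaacetate. Section 1.2 gives that grade for both. The placebo sentence therefore leaves out at least one descriptor that does apply, which makes a second omission plausible.

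**What follows if the text is taken literally**

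Let A = 1 for quinine and 0 for placebo, B = 1 for a buffered vehicle and 0 otherwise, q the effect of quinine against the placebo additive, and b the effect of buffering. The treatment part of the outcome model is qA + bB. Compounding as written gives B = A for every patient, so

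qA + bB = (q + b)A.

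Only the sum q + b can be estimated.

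- Urn randomization (Section 5.3) balances patient characteristics between arms. It does not alter B = A.
- The mixed model (Section 6.5) has no patient with A and B different, so no covariate or random effect can separate q from b.

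**Sample size**

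Section 6.4 plans for a "precision of 10 (half the width of the desired 95% CI) to be 32 patients in each group", with an SD of about 20.

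- Normal critical value: n = 2 × (1.96 × 20 / 10)² = 30.7, rounded up to 31 per group.
- t critical value with 2n − 2 degrees of freedom: the half-width is 10.16 at n = 31 and 9.995 at n = 32, so the plan's 32 is reproduced.
- At 50 per group the t-based half-width is 7.94.

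A larger trial narrows the interval, but the interval stays centred on q + b. Stating one vehicle leaves the 32 unchanged.

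**Size of b**

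The documents give no effect of buffering on any endpoint, in either direction. There is no documented value to put in for b.

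**The case against.** The strongest reply is that this is a drafting slip. A vehicle not described as buffered has not been shown to be unbuffered. The placebo sentence visibly drops another qualifier, the authors use the word saline loosely even for the quinine arm, and buffered saline is in use in the study for technique practice. Nothing suggests that anyone chose two vehicles. Section 5.4 also gives preparation to the Investigational Drug Service, whose own formulation records are not part of this document and may already specify one vehicle. All of this stands, and it limits the point to an inconsistency in the specification.

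It does not dispose of the point. The section that defines the products leaves open whether the arms share a vehicle, and no other section answers it.

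A reader might go further in three ways that the documents do not support:

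- **That the comparison is in fact confounded.** This needs evidence of what was compounded, and the document has none.
- **That the false-positive rate rises by a stated amount.** Any such figure would come from an invented vehicle effect. The bias could also run against quinine and hide a benefit.
- **That tolerability or the blind is compromised.** Section 3.4 ties tolerability to bitterness, which is what Section 5.1 matches, and nothing in the documents says that the two salines would feel different in use.

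**Conclusion.** The point holds as an unresolved inconsistency in the product specification. Section 5.1 describes two vehicles where the stated contrast presumes one, and nothing else in the document resolves it. A dropped word is a plausible explanation.

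The consequence is conditional. If, and only if, the solutions were compounded as written, buffering and quinine cannot be told apart by the design or the analysis at any sample size. The size and direction of the resulting bias are unknown. The conclusion rests on the wording of Section 5.1 and on the absence of any statement that the vehicles are identical; it does not rest on an assumed effect of buffering. It is worth correcting because the attribution of any result to quinine depends on it and the correction is very cheap.

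**What to change.** - **Reconcile the two sentences in Section 5.1.** State that both arms are compounded from one identical saline vehicle and that only the bitter agent differs. Use the same description in Sections 1.4, 3.2 and 6.1 and in the pharmacy's compounding instructions.
- **Confirm from pharmacy records** which vehicle was used in each arm for any product already prepared, and report it.
- **If the vehicles do differ,** say in the protocol and the report that the contrast is between whole formulations, and do not attribute a difference to quinine alone.

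The cost is a short wording amendment and a check of compounding records. The sample size, visits and analysis model do not change.
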